14.1 Prior Anti-Cancer Therapies/Procedures

The prior anti-cancer treatments and procedures are collected under the Prior Anti-Cancer Drug Therapies Details, Prior Anti-Cancer Radiotherapies Details and Prior Anti-Cancer Surgeries Details eCRF pages.

The overall summary of prior anti-cancer treatments will include: the number and percentages of subjects by type of treatment, i.e.

- Number of subjects with at least one type of prior anti-cancer treatment
- Number of subjects with at least one prior anti-cancer surgery
- Number of subjects with at least one prior anti-cancer drug therapy
- Number of subjects with at least one prior anti-cancer radiotherapy

Summary of prior anti-cancer drug therapy will include the following variables for all the cohorts with exceptions for ovarian cancer cohort:

- Number of subjects with at least one prior anti-cancer drug therapy
- Number of any prior anti-cancer therapy lines: missing/ 1/ 2/ 3/ ≥ 4
- Number of any prior anti-cancer therapy lines as continuous variable
- Number of prior anti-cancer therapy lines for metastatic or locally advanced disease: missing/ 0/ 1/ 2/ 3/ ≥ 4 . If the intent of therapy is metastatic, locally advanced, or palliative, it will be counted into therapy lines for metastatic or locally advanced disease
- Number of prior anti-cancer therapy lines for metastatic or locally advanced disease as continuous variable
- Type of prior anti-cancer therapy: chemotherapy/ antibody therapy/ kinase inhibitors/ hormonal therapy/ vaccines/ bone marrow transplant/ lymphocyte infusion/ other
- Intent of therapy: adjuvant / neo-adjuvant / metastatic / locally advanced / palliative
- Best response: CR/ PR/ PD/ stable disease (SD)/ unknown/ not assessable (NE)/ not applicable. Best response is derived from the last treatment regimen

For secondary ovarian cancer cohort, one additional category will be defined for the following two variables:

- Number of any prior anti-cancer therapy lines: missing/ 1/ 2/ 3/ 4/ ≥ 5
- Number of prior anti-cancer therapy lines for metastatic or locally advanced disease: missing/ 0/ 1/ 2/ 3/ 4/ ≥ 5 .

For the primary gastric and GEJ cancer cohort, the following will be summarized for Not Progressed First Line Cancer (FLC) per drug category:

- Duration of latest prior anti-cancer regimen (Days)
- Duration of latest prior anti-cancer regimen start date to first study treatment (Days)

The prior anti-cancer drugs will also be extensively detailed with the number and percentage of subjects by the Anatomical Therapeutic Chemical (ATC) class level 2 and PT in a table. A subject will be counted only once within a given drug class and within a given drug name, even if he/she received the same medication at different times. If any prior anti-cancer medication is classified into multiple ATC classes, the medication will be summarized separately under each of these ATC classes. In case any specific medication does not have ATC classification level 2 coded term, it will be summarized under “Unavailable ATC classification” category. The summary will be sorted on decreasing frequency of drug class and decreasing frequency of drug name in a given drug class, based on the incidence in the “Overall” column. In case of equal frequency regarding drug class (respectively drug name), alphabetical order will be used.

The listings of prior anti-cancer treatments and procedures will also be provided: a) listing of prior anti-cancer drug therapies, b) listing of prior anti-cancer radiotherapies, and c) listing of prior anti-cancer surgeries. These will include subject identifier and all the relevant collected data-fields on the corresponding eCRF pages.

14.2 Prior and Concomitant Medications/Procedures

Prior and concomitant procedures are collected on the Concomitant Procedures Details eCRF page. Prior and concomitant medications are collected on the Concomitant Medications Details eCRF page.

Medications started prior to first dose date of study treatment and continued into the on-treatment period as well as those started during on-treatment period are referred to as concomitant medications. Prior medications are defined as the medications started and stopped prior to the first dose date of study treatment. Post medications are defined as any medications started after on-treatment period.

Summary of concomitant medications will include the number and percentage of subjects by ATC classification level 2 and PT. A subject will be counted only once within a given drug class and within a given drug name, even if he/she received the same medication at different times. If any concomitant medication is classified into multiple ATC classes, the medication will be summarize separately under each of these ATC classes. In case any specific medication does not have ATC classification level 2 coded term, it will be summarized under “Unavailable ATC classification” category. The summary of concomitant medications will be sorted on decreasing frequency of drug class and decreasing frequency of drug name in a given drug class, based on the incidence in the

“Overall” column. In case of equal frequency regarding drug class (respectively drug name), alphabetical order will be used.

Prior and concomitant medication data will be listed from the Concomitant Medications eCRF page. Following variables will be included in the prior and concomitant medication listing: subject identifier, prior/ concomitant/ post medication, and all corresponding data field on the corresponding eCRF page.

Prior and concomitant procedures data will be listed from the Concomitant Procedures Details eCRF page. Subject identifier and all collected data-field on the corresponding eCRF page will be included in the listing.

14.3 Subsequent Anti-Cancer Therapies/Procedures

Anti-cancer treatment after discontinuation will be provided in a data listing with data retrieved from Anti-Cancer Treatment After Discontinuation, Radiotherapy After Discontinuation, and Surgery After Discontinuation eCRF pages. A table for anti-cancer treatment after discontinuation will be added for primary analysis.

15 Treatment Compliance and Exposure

Analysis of exposure will be based on the calculated actual dose levels (total dose administered/weight, mg/kg). The last non-missing weight of the subject on or prior to the day of dosing will be used for the calculation.

The summary of treatment exposure and compliance based on the SAF analysis set will include the following variables per subject (a cycle refers to the planned dosing interval of two weeks):

- Treatment duration (in weeks), defined as $(\text{the last dose date} - \text{the first dose date} + 14)/7$
- Number of administrations as continuous variable
- Cumulative dose (mg/kg), defined as sum of actual dose levels
- Dose intensity (mg/kg/cycle), defined as $\text{cumulative dose (mg/kg)} / (0.5 * \text{treatment duration (week)})$
- Relative dose intensity (%), defined as $\text{actual dose intensity (mg/kg/cycle)} * 100 / \text{planned dose level (mg/kg/cycle)}$.
- Relative dose intensity by the following categories:
 - >0.9
 - $>0.8-0.9$
 - ≤ 0.8

Individual relative dose intensity (%) is calculated as $\text{actual dose level (mg/kg)} / \text{planned dose level (mg/kg)} \times 100$ for each administration of study medication. A dose reduction is defined as actual non-zero dose $< 90\%$ of planned dose, or individual relative dose intensity $< 90\%$. A table based

on SAF will be prepared to summarize the number and percentage of subjects with at least one dose reduction, and a breakdown by the number of dose reductions (1/2/3/≥4).

Per protocol, avelumab will be administered as 1-hour i.v. infusion. Subjects will receive the study treatment once every 2 weeks. Dose delays will be grouped into the following categories based on the deviation of the actual to the planned treatment administration day (relative to the previous non-zero dose date): no delay (including 1-2 days delays), 3-6 days delay, 7 or more days delay. For example, if one subject receives the study treatment on day 1, then the next study treatment administration date will be on day 15; however, if the subject receives the study treatment at day 16 or 17, this is considered as 'no delay'. Any zero dose prior to the last treatment administration is considered as a dose interruption.

The summary of dose delays will be based on the SAF and include the following categories:

- No delay
- 3-6 days delay
- 7 or more days delay

The categorization is based on the maximum length of delay, i.e. the worst case of delay if subjects have multiple dose delays.

A listing of study treatment administration will include subject identifier, study day, # of days relative to prior treatment, infusion rate, most recent body weight prior to infusion, actual/planned dose, batch ID, dose reduction/dose delay or interruption, and other relevant information collected on the Cohort Treatment MSB0010718C Administration Details eCRF page. A subset of this listing will be created for subjects with at least one dose reduction.

A listing of treatment exposure and compliance will include subject identifier, assigned dose level, and above derived variables summarized in the tables.

In order to mitigate infusion-related reactions, a premedication regimen of 25 to 50 mg diphenhydramine and 650 mg acetaminophen (i.v. or oral equivalent) is mandatory 30 to 60 minutes prior to each dose of study treatment starting on January 29, 2014. The compliance to this requirement will be summarized as numbers of subjects with 0, 1, 2, 3, 4 doses among the first 4 treatment administrations that were administered without pre-medication. For example: if a subject discontinued after 3 doses, and 2 of them were administered with premedication, the number for that subject would be 1.

A listing of premedication will include subject identifier, reported medication term, the relative time to the start of infusion, date/time of premedication, and dose (unit). A listing containing subject identifier, visit, and unique study treatment batch ID will also be created.

16 Endpoint Evaluation

The subsections in this section include specifications for analyzing clinical trial endpoints specified in the Clinical Trial Protocol to meet the trial objectives, as well as any endpoints not identified in the Clinical Trial Protocol.

The primary endpoint for expansion phase is

- The confirmed BOR, per RECIST 1.1, as adjudicated by an IERC for subjects enrolled in the efficacy expansion cohorts only, which is addressed in the [Section 16.1](#).

The secondary endpoints (excluding AE) for expansion phase are:

- irBOR and BOR according to modified irRC and to RECIST 1.1 criteria, respectively, per investigator assessment.
- The confirmed BOR, per RECIST 1.1, as adjudicated by an IERC for subjects enrolled in the urothelial carcinoma secondary cohort.irPFS time and PFS time according to modified irRC and to RECIST 1.1 criteria, respectively, per investigator assessment.
- OS time.
- For the primary expansion cohorts only: Unconfirmed response at Week 13 according to RECIST 1.1 criteria, per investigator assessment.
- DR according to modified irRC and to RECIST 1.1 criteria, respectively, per investigator assessment.
- TTR according to modified irRC and to RECIST 1.1 criteria, respectively, per investigator assessment.
- For the efficacy expansion cohorts and the urothelial carcinoma secondary cohort:
 - PFS time, according to RECIST 1.1, per IERC
 - DR according to RECIST 1.1, per IERC
 - TTR according to RECIST 1.1, per IERC
- PK profile.
- Pharmacodynamic profile
- Serum titers, isotypes, and neutralizing capacity of anti-avelumab antibodies.
- Expression of PD-L1 on tumor tissue.

Secondary efficacy endpoints are addressed in [Section 16.2](#). The secondary endpoints PK and immunogenicity are addressed in [Section 16.4](#) and [16.5](#), respectively. CCI

[REDACTED]

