As of 05 November 2014, a cumulative review revealed 56 cases of potential immune-related AEs out of 480 subjects (11.7%) treated in the dose expansion part of trial EMR 100070-001 and 4 cases out of 50 subjects (8.0%) treated in the dose escalation part of trial EMR 100070-001. A customized Medical Dictionary for Regulatory Activities (MedDRA) query was used for data retrieval from the clinical database with predefined Preferred Terms of potential immune-related AEs (irAEs).

Of 69 potential irAEs reported, 13 were SAEs (18.8%) and 56 were non-serious AEs (81.1%). In the majority of the cases, there was a plausible temporal association between the event onset and the drug administration. Of these 69 events, 46 events (66.7%) were assessed as treatment-related by the investigator and 23 events (33.3%) were assessed as not treatment-related by the investigator.

Twenty-six events were assessed as Grade 1, 29 events as Grade 2, 11 events as Grade 3, 2 events as Grade 4, and 1 event (pneumonitis) as Grade 5 (Please note: 2 more events of autoimmune

hepatitis had a fatal outcome; however, they were assessed as Grade 3 with a consequent fatal liver failure).

Based on the irAE cases that have been observed, all trial investigators have been trained to be made aware of the frequency and severity of the observed events and to proactively administer steroid treatment for any suspicion of irAEs. Of note, irAEs are considered as an identified risk by the Sponsor.

Infusion-related Reactions

Two suspected unexpected serious adverse reactions (SUSARs; anaphylactic reaction and infusion-related reaction) involving 2 subjects were reported in December 2013 and triggered a cumulative review of serious and non-serious cases of infusion-related reactions / hypersensitivity across the avelumab program. Following evaluation of safety signals, infusion-related reactions / hypersensitivity have been classified as a newly identified risk (previously classified as a potential risk) and a mandatory premedication regimen of histamine H1 receptor (H1) blockers plus acetaminophen was implemented for all trial subjects as of 28 January 2014.

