
Trial Product
	
Avelumab will be administered as 1-hour intravenous (i.v.) infusion. Subjects will receive avelumab once every 2 weeks until confirmed progression, unacceptable toxicity, or any criterion for withdrawal from the trial or IMP occurs.
 
The dose of avelumab will be calculated based on the weight of the subject determined on the day of each drug administration.
 
Premedication with an antihistamine and with paracetamol (acetaminophen) approximately 30 to 60 minutes prior to each dose of

	
avelumab is mandatory (for example, 25-50 mg diphenhydramine and 500-650 mg paracetamol [acetaminophen] i.v. or oral equivalent). This regimen may be modified based on local treatment standards and guidelines, as appropriate.
 
Immediate access to intensive care unit or equivalent environment and appropriate medical therapy (including intravenous epinephrine, corticosteroids, antihistamines, bronchodilators, and oxygen) must be in place for use in the treatment of potential infusion reactions. Infusion of avelumab will be stopped in case of \geq Grade 2 infusion-related, allergic, or anaphylactic reactions (according to NCI-CTCAE v4.0). Following avelumab infusion, subjects must be observed for 2 hours post infusion for potential infusion-related reactions (IRRs).

Treatment and Trial Duration
	
The planned treatment duration is until unacceptable toxicity, or any criterion for withdrawal from the trial or IMP occurs.

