8.2 Safety Analysis for Interim CSR

The purpose of analysis is to support comprehensive safety review of avelumab in the ongoing trials, the results will be included into an interim CSR.

- The analysis for the interim CSR will be based on a data cut-off date of 20Nov2015.
- The data to be included into the first interim CSR are demographics and baseline characteristics, prior anti-cancer therapy, concomitant medication and procedure, drug exposure and compliance, premedication, safety parameters (AEs, lab, vital signs, electrocardiograms [ECGs], and Eastern Cooperative Oncology Group [ECOG]), immunogenicity, and PK.
- The data will be pooled across all the expansion cohorts for the analysis.
- The safety analysis set (SAF) used for the analysis will contain all the expansion subjects who receive at least one dose of study treatment by the data cut-off date.

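### The expansion SAP's premedication compliance table has no date limit, so unpremedicated doses given before the January 2014 requirement would count as non-compliance

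*SAP*

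**What the plan says.** Expansion SAP Section 15 (Treatment Compliance and Exposure) describes a premedication regimen that "is mandatory 30 to 60 minutes prior to each dose of study treatment starting on January 29, 2014". The next sentence begins "The compliance to this requirement will be summarized as numbers of subjects with 0, 1, 2, 3, 4 doses" and limits these to doses "among the first 4 treatment administrations that were administered without pre-medication". Its worked example is: "if a subject discontinued after 3 doses, and 2 of them were administered with premedication, the number for that subject would be 1".

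Expansion SAP Section 8.2 lists premedication among the contents of the first interim report. It pools all expansion cohorts and uses a safety set that "will contain all the expansion subjects who receive at least one dose of study treatment by the data cut-off date". It excludes nobody by date of first dose.

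The protocol (Section 3.4, Infusion-related Reactions) says that the premedication regimen "was implemented for all trial subjects as of 28 January 2014", one day earlier than the SAP. The same protocol section, in its account of expansion subjects who discontinued, says that most of the infusion-related and anaphylactic reactions behind those discontinuations happened before that date.

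The dose-escalation SAP, also in its Section 15, specifies the same tabulation but calls it the use of premedication, not compliance.

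**The concern.** A compliance table should count failures among the doses to which the rule applied. This one counts every unpremedicated dose among the first four, whenever it was given. A subject first treated in autumn 2013 without premedication, and premedicated at every dose once the rule existed, would be shown as missing up to four mandatory premedications. In cohorts that opened early, the result would then depend partly on enrolment date and not only on whether sites followed the rule. The requirement was a safety measure introduced after two unexpected serious reactions, so a table labelled as compliance with it should measure just that.

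**Working it through.** **The plan's own example.** Three doses received, two premedicated: 3 − 2 = 1. This reproduces the SAP's figure. No dose date enters the calculation.

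**Inputs**
- Start of the requirement: 29 January 2014 (both SAPs, Section 15); 28 January 2014 (protocol Section 3.4).
- First 90 NSCLC subjects: median follow-up 6 months, range 3 to 10, at the 17 July 2014 cut-off (protocol Section 3.5.4).
- Dosing every 14 days, so dose 4 falls 3 × 14 = 42 days after dose 1.
- 1 month = 30.4375 days (SAP convention). Follow-up is assumed to run from first dose to cut-off, as the expansion SAP defines it.

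**Dates.** First dose = 17 July 2014 − follow-up in months × 30.4375 days. Count the first four doses that fall before 29 January 2014, with no dose delays.

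| Follow-up (months) | Dose 1 | Dose 4 | Doses before 29 Jan 2014 |
|---|---|---|---|
| 10 | 16 Sep 2013 | 28 Oct 2013 | 4 |
| 6.97 | 17 Dec 2013 | 28 Jan 2014 | 4 |
| 6.5 | 31 Dec 2013 | 11 Feb 2014 | 3 |
| 6 | 15 Jan 2014 | 26 Feb 2014 | 1 |
| 5.5 | 31 Jan 2014 | 14 Mar 2014 | 0 |
| 3 | 17 Apr 2014 | 29 May 2014 | 0 |

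With the protocol's date of 28 January, a dose given on that day falls under the rule. The 6.97-month row then drops from 4 to 3 and the 6.5-month row from 3 to 2.

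**How many subjects.** From 28 January to 17 July 2014 is 170 days, and 170 / 30.4375 = 5.59 months. If the true median exceeds 5.59 months, at least half of the 90 (45) had their first dose on or before 28 January. A median reported as 6 could lie anywhere from 5.5 to 6.5, so this holds over most, but not all, of the rounding range. Later NSCLC subjects are unaffected: the 90th started 13 weeks (91 days) before the cut-off, about 17 April 2014.

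**As a share.** 45/90 = 50% of the first 90; 45/184 = 24% of the NSCLC subjects treated by 5 November 2014 (protocol Section 3.4); 45/1640 = 2.7% of the planned expansion total. These are subjects who may have a pre-rule dose. Only those whose pre-rule doses also lacked premedication are miscounted.

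**Effect on one subject.** Take four doses, with every pre-rule dose unpremedicated and every later dose premedicated.

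| Pre-rule doses | Score as written | Score with a date limit |
|---|---|---|
| 1 | 1 | 0 of 3 |
| 2 | 2 | 0 of 2 |
| 3 | 3 | 0 of 1 |
| 4 | 4 | no dose under the rule |

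**The case against.** The best defence is that the table is to describe compliance with a requirement whose start date stands in the sentence before, so a sensible programmer would leave earlier doses out. The table shells are not available and may contain such a filter. Read simply as a count of premedication use, the tabulation is correct, and only its label misfits. No endpoint, test, futility rule or analysis set depends on it. These points settle the weight of the matter, but the stated algorithm and its example still carry no date limit, and the SAP is the specification to be programmed.

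A reader might infer more than the documents support:
- **That compliance could not be assessed at all.** Section 15 also plans listings with the date and time of each premedication and details of each study drug administration, so pre-rule doses can be identified. Unpremedicated doses after the start date remain in the count.
- **That about a quarter of NSCLC subjects would be shown as non-compliant.** The 24% rests on a rounded median, and the documents do not say how many early doses lacked premedication.
- **That the breast cancer cohort is equally affected, or that the effect then disappears.** The documents give no start dates for breast cancer subjects relative to January 2014 and no basis for a time pattern in the results.
- **That the infusion-reaction analysis is biased.** Expansion SAP Section 17.1.4 splits reactions by actual presence or absence of premedication, so the missing date limit does not touch it.
- **That a 500 mg acetaminophen dose would be scored as no premedication.** Section 15 sets no milligram threshold for the count. The text differs (650 mg there, "500-650 mg paracetamol" as an example in Section 6), but the difference does not enter the tabulation.

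**Conclusion.** The point holds as a specification gap with a small, local effect. Followed literally, Section 15 of the expansion SAP counts unpremedicated pre-rule doses as non-compliance. The protocol confirms that expansion subjects were treated before the rule: the longest-followed of the first 90 NSCLC subjects would have had all four counted doses by late October 2013. Roughly half of those 90 may have at least one pre-rule dose, assuming two-weekly dosing without delays and follow-up measured from first dose. The true number, and the number actually miscounted, cannot be obtained from the documents. The distortion matters mainly in a cohort-level table. Pooled over all expansion cohorts, the NSCLC contribution is about 3%, and any contribution from other early cohorts cannot be estimated. No confirmatory result is affected.

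**What to change.** In expansion SAP Section 15, count only administrations on or after the implementation date. Report for each subject how many of the first four doses fell under the requirement, as the denominator, and show pre-rule doses in a separate column. If that is not wanted, at least relabel the table as use of premedication, as in the escalation SAP.

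Two inconsistencies should be settled at the same time:
- The start date is 28 January 2014 in the protocol and 29 January 2014 in both SAPs. A date filter needs one date.
- The acetaminophen wording is 650 mg in Section 15 of both SAPs, but a 500 to 650 mg example, open to local modification, in protocol Section 5.1.3 and expansion SAP Section 6. These passages must be reconciled; this review does not say which is right.

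The cost is one SAP sentence and a date filter in the program. No new data are needed, because the planned listings already use the dates.
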